## 9.2 Safety Parameters

### 9.2.1 Safety Parameters

Safety parameters will include all AEs reported, radiographic stability at 1, 2 and 5-year visits and revision rates.

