## Primary:

	A one-sided 95% confidence interval of the total KSS change from preoperative to 2 years postoperative (2 years - preoperative) will be computed at 2 years postoperative. For the non-inferiority comparison, the lower bound of this confidence interval will be compared with 63 points (10% worse than the expected improvement). For the superiority comparison, the lower bound of this confidence interval will be compared with 70 points (the expected improvement).
Statistical Methodology	Secondary:
	An independent group t-test or a nonparametric test will be used to
	compare the secondary numerical parameters (e.g. KSS, HSS, KOOS)
	between the JL restoration subgroups at 1, 2 and 5 years
	postoperative; and a Chi-square test or Fisher's exact test will be used
	to compare the secondary categorical parameters (e.g. postoperative
	stability, anterior knee pain and functional performance) between the
	subgroups. In addition, a paired t-test or Wilcoxon rank sum test will be
	used to compare the change in outcomes other than the KSS from
	preoperative to 1, 2 and 5 years postoperative within the Triathlon TS
	Total Knee System group. The radiographic stability rates, adverse
	event (AE) rates and revision rates with 95% confidence intervals will
	be presented in tables.

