### CONFIDENTIAL

### 2.1.2 Secondary

The secondary objectives of this study will be to evaluate the effect of JL restoration on revision TKR with specific reference to effect on postoperative stability, anterior knee pain and functional performance at 2 and 5 years postoperatively. It is expected that the Triathlon® TS group with JL elevation > 5 mm is non-inferior to the Triathlon TS group with JL elevation  $\leq$  5 mm.

All outcomes other than the change in KSS, already analyzed as the primary objective, will be analyzed from preoperative to 1, 2 and 5 years postoperatively.

Additionally, the long-term performance of the Triathlon TS Total Knee System for revision TKR will be evaluated with regard to radiographic stability, revision rate and complications when reviewed against published data.

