### Radiographic Outcomes

### CONFIDENTIAL

Radiographs will be taken and collected in the AP, ML, and Merchant (30° of flexion) views for the preoperative, 6-week, 1, 2 and 5-year intervals. See Appendix B for the radiographic technique to be used.

Radiographs will be evaluated by an independent reviewer for radiolucency of all components, and subsidence for the tibial and femoral components of the Triathlon TS Total Knee System. JL measurements will also be taken according to Appendix A.

Patellar component positioning will be assessed to determine the presence of tilt and/or displacement. Parameters for radiographic failures will follow the guidelines that have been set by the Knee Society. The scoring system for each of the three components is determined by measuring the width of the radiolucent lines for each of the zones in millimeters for each of the three components. The total widths are added for each zone for each of the three prostheses. The total produces a numerical score for each component. Failure is defined as a score of 10 or greater, regardless of symptoms. A migrating or shifting prosthesis, with or without the disappearance of radiolucent lines, should be considered as a possible or impending failure regardless of the score.

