### CONFIDENTIAL

For categorical variables, such as radiographic stability, revision rates and complications, the number and percent in each category will be presented.

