### CONFIDENTIAL

Revision or removal of a femoral component or tibial baseplate constitutes a failure and study termination for the subject.

If tibial insert exchange is required during the study, the event is considered a reoperation and does not constitute a failure or study termination.

Patellar component revision at the time of study surgery is optional. However, if the subject requires patellar component revision a Triathlon Patellar Component must be used.

If the patellar component is not revised at the time of study surgery and is later revised, it must be revised to a Triathlon Patellar Component. This event is considered a reoperation and does not constitute a failure or study termination.

If a Triathlon Patellar Component is implanted at the time of study surgery and is revised again during the course of the study, the event is considered a reoperation and does not constitute a failure or study termination. A Triathlon Patellar Component must be used.

Use of ancillary devices at the time of study surgery is optional. However, if the patient requires ancillary devices, the protocol-specified components must be used.

If ancillary devices are not used at the time of study surgery and are needed at a later date during the course of the study, protocol-specified components must be used. This event is considered a reoperation and does not constitute a failure or study termination.

If any protocol-specified ancillary devices implanted are revised or removed at a later date, this would constitute a removal but would not result in failure or termination.

If the subject fails to return for their follow-up appointments, every effort should be made to contact the subject to assess his/her health status. If after attempting to contact the subject through three documented phone calls and a certified letter, the subject still does not respond, he/she will be considered lost to follow-up. A Study Termination CRF will be completed only after notifying Stryker of the subject's status and being given approval to terminate.

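### Per-visit radiographic stability loses cases already revised for loosening, so read as a rate for all implanted cases it overstates stability by about the share so revised

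*Combined protocol and SAP*

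**What the plan says.** Section 2.1.2 makes stability a secondary objective, to be judged through "radiographic stability, revision rate and complications when reviewed against published data". Under Radiographic Outcomes, the same section scores the width of radiolucent lines for each of three components: "Failure is defined as a score of 10 or greater, regardless of symptoms". It treats a migrating or shifting component only as a warning of failure, whatever its score. Films are scheduled before surgery, at 6 weeks, and at 1, 2 and 5 years.

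Section 9.2.1 lists the safety outcomes: "Safety parameters will include all AEs reported, radiographic stability at 1, 2 and 5-year visits and revision rates". Section 9.2.2 gives the summary: "For categorical variables, such as radiographic stability, revision rates and complications, the number and percent in each category will be presented". The synopsis adds 95% confidence intervals for stability, adverse event and revision rates. No section states the denominator for stability.

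Section 10.3 rules that "Revision or removal of a femoral component or tibial baseplate constitutes a failure and study termination for the subject", and dates the termination to the procedure. The patella is treated differently: "If a Triathlon Patellar Component is implanted at the time of study surgery and is revised again during the course of the study, the event" counts as a reoperation and follow-up continues. Section 9.3 rules out imputation in the primary and secondary analyses. Section 9.4.4.3 defines a population of all enrolled subjects who received the device, for a survival analysis whose endpoint and method are not described.

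**The concern.** Stability is read from films, and a removed femoral component or baseplate has no later study film. The components that failed badly enough to be taken out are thus absent from the stability table at every visit after their removal. Section 10.3 calls these cases failures, yet the radiographic result has no place for them.

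The gap is widest between 2 and 5 years, when no film is scheduled. A component sound at 2 years that loosens and is revised at 4 years counts as stable at 2 years and is missing at 5.

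At stake is the meaning of a figure that gets its own confidence interval and its own comparison with the literature. A reader will tend to take the 5-year percentage as describing the implanted group, when it describes implants still in place and filmed. The error always favours the device.

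**Working it through.** **1. The plan's own figures.** The documents give no figure for radiographic stability or for revision for loosening. The nearest usable base is the sample size in Section 9.4.2. With SD 35, margin 7, one-sided alpha 0.05 and 80% power, n = (35 × (1.6449 + 0.8416) / 7)² = (12.432)² = 154.56, against 154 stated. Allowing 15% loss, 154 / 0.85 = 181.2, against 181 stated. I use 154 as an illustrative number of cases with known status at a visit. Fewer may remain at 5 years, but the result depends on shares rather than on this base.

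**2. What happens to a case that loosens.** I take stable to mean not failed under the definition in Section 2.1.2; the plan does not spell this out.

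- Failing on a 1- or 2-year film, revised later: counted unstable at that visit, absent afterwards.
- Loosens and is revised between two films: may be counted unstable at no visit.
- Failing on film, not revised, still attending: counted at each visit.

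**3. Formula.** Let N be cases with known status, R those revised for loosening before the visit, and U those unstable on film among the rest.

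- Per-visit percent stable: P = (N − R − U) / (N − R)
- Percent neither failed on film nor revised for loosening: C = (N − R − U) / N
- Gap: P − C = P × R / N

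Because P is close to 1, the gap is close to R/N, the share revised for loosening.

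**4. Numbers.** R and U are assumptions. With N = 154 and U = 3 (gaps taken before rounding):

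| R (share of 154) | Per-visit, P | Counting revisions, C | Gap (points) |
|---|---|---|---|
| 0 (0.0%) | 151/154 = 98.1% | 151/154 = 98.1% | 0.0 |
| 3 (1.9%) | 148/151 = 98.0% | 148/154 = 96.1% | 1.9 |
| 5 (3.2%) | 146/149 = 98.0% | 146/154 = 94.8% | 3.2 |
| 8 (5.2%) | 143/146 = 97.9% | 143/154 = 92.9% | 5.1 |
| 15 (9.7%) | 136/139 = 97.8% | 136/154 = 88.3% | 9.5 |

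Exact 95% intervals for R = 5 are 94.2 to 99.6 (P) and 90.0 to 97.7 (C). For R = 8 they are 94.1 to 99.6 and 87.6 to 96.4. With U = 8 the gaps hardly change: 1.8, 4.9 and 9.2 points for R = 3, 8 and 15.

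**5. Why a simple pooled ratio is not the remedy.** One could divide all failures to date by cases with a film plus earlier failures. That keeps every earlier failure but drops lost cases that had not failed, so it errs the other way. Assume 130 cases with 5-year films, 4 failing, and 8 earlier revisions for loosening. The ratio is (4 + 8) / (130 + 8) = 12/138 = 8.7%. If the 8 arose among all 181 implanted before other losses, the cumulative figure is 1 − (1 − 8/181)(1 − 4/130) = 1 − 0.9558 × 0.9692 = 7.4%. A time-to-event estimate handles the losses properly.

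**The case against.** The strongest reply is that nothing is hidden. The sentence that lists stability also lists revision rates, and Section 9.2.2 tabulates both. The synopsis puts intervals on both, Section 2.1.2 names them together, and Section 8.3 requires revisions to be reported within 24 hours. Film status of implants still in place, shown beside the revision rate, is a legitimate summary. The table is descriptive and carries no test or decision rule.

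Most of this stands, and it keeps the point modest. It does not remove it. The revision rate is not split by cause, and nothing links film failures to revisions case by case. A reader therefore cannot combine the two tables into the share of implants that failed by loosening. The survival population in Section 9.4.4.3 could supply this, but no endpoint is attached to it.

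Four stronger readings are tempting, and the documents do not support them:

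- **That a loosened, revised component never appears as unstable.** One already failing on a 1- or 2-year film is counted at that visit.
- **That the plan specifies a survivors-only denominator.** It specifies none. Film-based scoring, termination at revision and the absence of carry-forward make that the natural execution, but it is an inference.
- **That every revision removes the case.** Re-revision of a patellar component does not end participation, so the mechanism is confined to the femoral component and baseplate.
- **That more revisions for loosening make the stability rate look better.** In the table above, the per-visit figure stays almost flat (98.1% to 97.8%). What grows is its distance from the figure for the whole group.

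It also cannot be seen from the documents whether the published series count revisions within radiographic failure, so the effect on that comparison is unknown.

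**Conclusion.** The point holds in a limited form. As planned, the per-visit percentage has no stated denominator and no place for a femoral component or baseplate removed for loosening before the visit. As a description of unrevised implants with films it is sound. As an estimate for all implanted cases it is biased upward whenever such revisions occur, by about the share so revised: nil with none, about 3 points at 3.2%, and about 9.5 points at 9.7%.

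These sizes rest on assumed numbers of revisions and film failures, since the documents give neither. It would go too far to say that the reported rates will be too high; they will be if any such revision occurs. The matter is worth correcting because the result is to be set against published data and the remedy is small.

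**What to change.** In Section 9.2.2:

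1. Keep the per-visit table at 1, 2 and 5 years. State its denominator and label it as unrevised cases with films.
2. Add the cumulative incidence, with 95% confidence interval, at 1, 2 and 5 years of the first of two events: radiographic failure (a score of 10 or more, as in Section 2.1.2), or revision or removal for loosening or migration. Base it on all implanted cases (the Section 9.4.4.3 population). Treat death and revision for other reasons as competing events, and censor lost cases at their last film. The Safety population is less suitable, because Section 9.4.4.4 removes cases with deviations that could affect outcome, and Section 11.6 lists an unavailable primary endpoint as a deviation. A case revised before 2 years might be removed on that ground.
3. Show migration without a score of 10 on a separate line, since Section 2.1.2 does not class it as definite failure.

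The cost is one extra table, coding the reason for revision from the adverse event and revision reports, and a possibly less favourable figure. The case report forms were not available for this review, so whether they already record the reason for revision should be checked. No extra visit or film is needed.

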## 9.2.2 Safety Analysis

All AEs will be listed, tabulated and summarized by event, number and percent of cases/subjects. AE rates and 95% confidence intervals will be presented. In addition, a Fisher's exact test will be used to compare the AE rates between the subgroups or cohorts, if appropriate.

### CONFIDENTIAL

For categorical variables, such as radiographic stability, revision rates and complications, the number and percent in each category will be presented.

## 9.3 Missing Data

No missing data will be imputed for the primary analysis and secondary analyses.

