### CONFIDENTIAL

## 9.1.4 Primary Efficacy Analysis

A one-sided 95% confidence interval of the total KSS change from preoperative to 2 years postoperative (2 years - preoperative) will be computed at 2 years postoperative. For the non-inferiority comparison, the lower bound of this confidence interval will be compared with 63. For the superiority comparison, the lower bound of this confidence interval will be interval will be compared with 70.

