### 9.4.2 Sample Size Calculation

A total of 181 cases implanted with the Triathlon TS Total Knee System will be enrolled in the study. The mean total KSS improvement expected, as compared from preoperative to 2 years postoperative, is 70 points. It is assumed that the mean total KSS improvement from preoperative to 2 years postoperative for cases implanted with the Triathlon TS Total Knee System will be comparable to the expected rates (not 10% or 7 points worse), above 63 points. Given a standard deviation of 35 for the improvement in scores, 80% power, and a one-sided 0.05 alpha level to test the 10% (7 points) non-inferiority hypothesis, a sample size of 154 subjects will be required to meet the primary efficacy objective. By factoring in a 15% lost to follow-up rate within 2 years, a total enrollment of 181 subjects will be needed.

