### 9.4.4 Efficacy Patient Populations

### 9.4.4.1 Efficacy

**Per Protocol Population**: The study population for analysis will include all subjects who receive the Triathlon TS Total Knee System. This does not include cases censored from analysis for a reason that may have a significant impact on outcome.

The primary and secondary efficacy analyses will be based on the per protocol population.

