### 9.4.4.3 Survival Analysis

Modified intent to treat population: Subjects enrolled in the study who received the Triathlon TS Total Knee System will be included in the survival analysis.

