## 10.3 Early Withdrawal of Subjects

### When and How to Withdraw Subjects

In the event that a subject is discontinued by the investigative center prior to the final study evaluation, the subject will be notified by the center that they are no longer in the study and a Study Termination CRF will be completed.

The following is a list of reasons for which subjects may be withdrawn and the date of termination that should be used on the Study Termination CRF in each situation. This list is not all inclusive:

Termination Reason	Date of Termination
Death	Date of death
Investigative center termination	Date of study close-out visit
Lost to follow-up	Date Stryker termination approval given
Voluntary withdrawal	Date subject notified center of withdrawal
Revision/removal of study device	Date of revision/removal procedure
Study device not implanted	Date of surgery
Surgery not performed	Date Stryker termination approval given

At the time of study surgery it is required that the following components are implanted:

- Triathlon TS Femoral Component
- Triathlon TS Universal Tibial Baseplate
- Triathlon TS Plus Tibial Insert or Triathlon PS Tibial Insert

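### Femoral or baseplate failures before 2 years drop out of the primary KSS mean, and no pre-specified analysis shows whether non-inferiority depends on their absence

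*Combined protocol and SAP*

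**What the plan says.** Section 10.3 (Early Withdrawal of Subjects) states: "Revision or removal of a femoral component or tibial baseplate constitutes a failure and study termination for the subject". Its table of termination dates gives, for revision or removal of the study device, "Date of revision/removal procedure". Insert exchange, patellar revision and later changes to ancillary devices do not terminate the subject.

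Section 9.1.4 defines the primary analysis: "A one-sided 95% confidence interval of the total KSS change from preoperative to 2 years postoperative (2 years - preoperative) will be computed". The lower bound is compared with 63 for non-inferiority and 70 for superiority. Section 9.3 adds: "No missing data will be imputed for the primary analysis and secondary analyses".

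The efficacy population in section 9.4.4.1 is broad at first reading: "The study population for analysis will include all subjects who receive the Triathlon TS Total Knee System". Cases censored for a reason that may affect outcome are then removed. Section 9.4.4.4 applies this to protocol deviations that could affect outcome and has those cases reported separately. Section 11.6 lists an unavailable primary endpoint among the deviations. The text does not say whether a revised case falls under this rule.

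Failures are visible elsewhere. Section 9.2.2 states: "For categorical variables, such as radiographic stability, revision rates and complications, the number and percent in each category will be presented". The synopsis adds 95% confidence intervals for revision rates. Section 9.4.4.3 defines a further population: "Subjects enrolled in the study who received the Triathlon TS Total Knee System will be included in the survival analysis". The only analysis called supportive is the optional ANCOVA between subgroups in section 9.1.5.

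**The concern.** Section 2.1.1 frames the primary objective around cases implanted with the system. The mean that decides the primary hypothesis can include only cases with a 2-year score. Among those missing are the cases the protocol itself calls failures, and their absence is tied to outcome. If failed knees would have scored lower, the completers' mean overstates the mean for all implanted cases.

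The revision rate and the KSS result will be reported side by side, but nothing pre-specified connects them. If the lower bound falls just above 63, the report as planned will not say whether a handful of early failures would have moved it below. Scores for failures chosen after the result is known would carry little weight.

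**Working it through.** **Inputs from the documents.** SD of the change 35, one-sided alpha 0.05, power 80%, margin 7 points, 154 evaluable, 15% loss, 181 enrolled (section 9.4.2); limits 63 and 70 (section 9.1.4).

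**Assumptions.** The documents give neither a failure rate before 2 years nor a KSS change for a failed knee. I use changes d of 0, +20, +35 and +50 points, the same for every failure, and let the number of failures k vary. With 154 completers and 181 implanted cases, k cannot exceed 181 − 154 = 27.

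**Step 1. The plan's own figures.** n = (35 × (1.645 + 0.842) / 7)² ≈ 154.6, against 154 stated. 154 / 0.85 = 181.2, against 181 stated. Both reproduce apart from rounding.

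**Step 2. Bound without failures.** SE = 35 / √154 = 2.820. With the t quantile 1.655 (153 df), the bound is M − 4.667. At an observed mean M = 70 it is 65.33, which is 2.33 points above 63. The smallest completer mean that passes is 63 + 4.667 = 67.67.

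**Step 3. Tipping point.** Add k failures at change d to 154 completers:

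- pooled mean m = (154M + kd) / (154 + k)
- pooled variance s² = [153 × 35² + 154(M − m)² + k(d − m)²] / (153 + k)
- bound = m − t(0.95; 153 + k) × s / √(154 + k)

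Example, M = 70, d = 0, k = 6: m = 10780 / 160 = 67.375, s = 36.83, bound 62.56. At k = 5 the bound is 63.002, still just above the limit.

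Smallest k that brings the bound to 63 or below, with the bound reached:

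| Completer mean (bound at k = 0) | d = 0 | d = +20 | d = +35 | d = +50 |
|---|---|---|---|---|
| 68 (63.33) | 1 (62.87) | 2 (62.72) | 2 (62.94) | 4 (62.98) |
| 70 (65.33) | 6 (62.56) | 8 (62.88) | 12 (62.99) | 27 (62.95) |
| 74 (69.33) | 14 (62.82) | 21 (62.86) | not within 27 | not within 27 |

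At a mean of 74 with all 27 remaining places taken by failures, the bounds are 63.9 (+35) and 66.3 (+50), so those scenarios cannot tip. The 27 in the middle row would need every case beyond the 154 completers to be a failure. As shares at a mean of 70, 6, 8 and 12 failures are 6/160 = 3.8%, 8/162 = 4.9% and 12/166 = 7.2%. If completers and failures together total 154, the counts at a mean of 70 become 5, 7 and 11.

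**Step 4. Error rate, under one reading only.** Suppose the 63-point limit applies to all implanted cases and their true mean is exactly 63. With failure share r, the completer mean is (63 − r·d) / (1 − r), and the chance of declaring non-inferiority is Φ((completer mean − 63) / 2.820 − 1.645).

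- r = 2%: completer mean 63.57 at d = +35, chance 7.5%; 64.29 at d = 0, chance 11.7%.
- r = 5%: completer mean 64.47 at d = +35, chance 13.1%; 66.32 at d = 0, chance 31.9%.

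The nominal rate is 5%. If the limit applies to completers, the rate stays at 5%.

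**The case against.** The complete-case rule is a disclosed choice in a single-arm, post-market study of a cleared device, and failures are not hidden: revision rates with confidence intervals and a survival population are planned. A reader might infer that the report would leave no way to judge the dependence. That goes too far. The calculation in step 3 needs only the completers' N, mean and SD and the number of failures, all of which should be reported. What a reader could not do is use the failed cases' own scores, and nothing obliges the sponsor to show the result.

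A reader might also infer a false-positive rate of up to about 80%. At 10% failures with zero change, step 4 does give 79.9%, but the implied completer mean is then 63 / 0.9 = 70, and 79.9% is simply the designed power at 70. It is an error only if the limit covers all implanted cases, and 10% within 2 years is an assumption.

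Nor do the documents show that the comparison favours the device. Section 9.4.2 says "The mean total KSS improvement expected, as compared from preoperative to 2 years postoperative, is 70 points" without stating whether the cited source left failures out. If it did, comparing completers with 63 is like with like.

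The terminating event is also narrow, since most reoperations keep the subject in follow-up. The 15% allowance does not answer the point: it is described as loss to follow-up and protects the sample size, not against informative missingness.

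These points limit the size and direction of the problem. They do not supply the missing analysis.

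**Conclusion.** The gap stands, as an inference from sections 9.1.4, 9.3 and 10.3 read together: a femoral or baseplate failure before 2 years has no 2-year KSS and cannot enter the primary mean, and no pre-specified KSS analysis shows what that does to the conclusion. It does not follow that the primary analysis is invalid, that its error rate is inflated regardless of how the limit is read, or that a revised case certainly stays in the efficacy population. The documents leave that last point open.

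The size rests on the assumed changes and on SD 35 with 154 completers. At the expected mean of 70, roughly 6 to 12 failures with changes between 0 and +35 would reverse non-inferiority. Near 68 one to four would do so, and at 74 only 14 or more with little or no improvement. The gap should be closed because doing so is cheap, and because the result is sensitive exactly where the decision would be close.

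**What to change.** Keep the complete-case primary analysis and the decision rule. In sections 9.3 and 9.1.4, pre-specify one non-gating supportive analysis:

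- Add femoral and baseplate failures before 2 years to the primary analysis set at zero change. Include any failure censored only because its 2-year score is unavailable.
- Show a tipping-point display against 63 over a range of assumed changes.
- Report both beside the primary result, with the number of failures.
- The last KSS before revision may be shown as a further scenario, with the caveat that it may predate the failure, since KSS is scheduled only at 6 weeks and 1 year before the 2-year visit.
- State that if the 70-point benchmark excluded failures, comparing this analysis with 63 is not like with like, and say which applies if the cited source allows.
- State whether a revised case counts as a deviation under sections 9.4.4.4 and 11.6.

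The cost is a few lines of plan text and modest programming on data already collected. No visits or patients are added, and sample size and power are unaffected. The downside is a little more analysis work and a supportive result that may be less favourable.
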